C.1.E. Preliminary data on cervical cancer screening in Mombasa County from the FP HIV SAIA trial show low screening and incomplete documentation. [name] has had discussions with key collaborators in Mombasa County including the Director of Health (see letter), noting that the majority of cervical cancer screening is conducted in either FP clinics or HIV clinics. The County's policy is that screening should be documented in the FP register. Cervical cancer screening is reported to the County for all clinics that receive County FP commodities. These data are compiled into the District Health Information System (DHIS). The quality of different data sources has not been formally evaluated. Preliminary results from the cervical cancer screening review linked to the FP HIV SAIA trial underscore the importance of the project proposed in the present application. The 60 clinics analyzed saw a mean of 204 FP clients per clinic (SD 172) during a 3-month period (a total of 12,236 clients over the three-month period of our data review). Of the 60 clinics, 4 (7%) did not record cervical cancer screening in the FP register, but reported recording it elsewhere. Because we did not review these alternative records in this initial survey, these clinics are excluded from subsequent analyses. Of the 56 remaining clinics, 7 (13%) recorded any cervical cancer screening. Only 120 women (1%) were screened. These preliminary data suggest few FP clinics perform cervical cancer screening, and that most women accessing FP services are probably not being screened for cervical cancer. Of the clinics offering screening, not all are documenting this activity in the FP register. Moving forward, data collected in outside logs could be entered into FP registers or abstracted separately. These preliminary data provide valuable information for this K08 proposal, which will comprehensively document screening practices in Mombasa County using all the available documentation sources. We will explore why screening prevalence and appropriate documentation is so low, and address this implementation gap with clinic-specific interventions using SAIA.

E. METHODOLOGY

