Procedures: Quantitative data: Initial information from intervention and control clinics will be obtained from clinic managers. Details about clinic characteristics such as size of the population served and what other services are provided will be collected. Staff characteristics will be collected including the number and type of staff, level of education, and experience of the clinic managers. Cervical cancer screening data will be collected from FP registers including screening method (VIA, visual inspection with Lugol's iodine [VILI], HPV with VILI, HPV alone, Pap smear), clients' HIV status, cervical cancer screening results (positive, negative, suspected), and information on referrals of positive or suspicious screens. These data will be collected at the beginning of the trial during a baseline period before any study procedures are completed, and then periodically every 3 months for all clinics.

Qualitative data: Qualitative IDIs will be conducted with clinic managers to understand cervical cancer screening practices and barriers. Study staff will explain the risks and benefits of participating in the IDIs and the procedures in place to safeguard their opinions. Clinic managers will then be asked to provide written informed consent to participate in an IDI. Types of questions study staff would ask include: "Describe what you know about cervical cancer screening.>"; "In your clinic, what do you think are barriers to screening more women for cervical cancer?"; "What are some ways that cervical cancer screening could be improved in your clinic?". These IDIs will be completed both prior to the trial and during the trial. Questions in the IDIs will be adapted from readily-available CFIR questions to understand where, when, and why the intervention works (50).

Randomization: Restricted randomization will be used to randomize FP clinics into intervention and control arms based on clinic size and location in Mombasa County(51). If facilities differ dramatically in cervical cancer screening rates at baseline, we will also stratify the randomization according to this factor.

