6. DATA MANAGEMENT

Aim 1:

Cervical cancer screening care cascade: The care cascade will examine the counts and proportions aggregated from the selected FP clinics as outlined in Figure 3. This cascade will account for appropriate exits from the cascade (e.g. outside screening age range, or screened negative) and losses in the cascade (e.g. not screened, or positive screen not referred for follow-up). Our research group has experience working with this type of complex care cascade in the setting of isoniazid prophylactic therapy for tuberculosis prevention, where there are multiple steps at which individuals can exit appropriately, be lost, or move on to the next step (55). We aim to model a cervical cancer screening care cascade in a similar manner.

Correlates of screening: Cervical cancer screening will be modeled as a binary outcome. Logistic regression will be used to examine correlates of screening including age, HIV status of clients, and specific clinic characteristics (detailed in Procedures). Analyses will be adjusted for any clustering by clinic.

Aim 2: The primary outcome is the proportion of all FP clients aged 21-65 years who were screened for cervical cancer over the total number of eligible clients. These outcomes will be assessed every 3 months in the 12-month study period. We are requesting an extension of the trial for an additional 6 months. Women who are not FP clients who are referred to a clinic solely for screening will be excluded as they could inflate the proportion of women screened. These women will be identified because they did not receive FP products or HIV testing and were only entered in the FP register because of screening. Generalized estimating equations with a binary link, clustered by clinic, will compare proportions screened in intervention versus control clinics longitudinally to account for correlation across time and between clinics. Interviews will be audio-recorded, transcribed, translated, coded for major themes, and analyzed using Dedoose software (56).

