7. VARIABLES – DEPENDENT, INDEPENDENT, CONFOUNDERS

Cervical cancer screening care cascade: The care cascade will examine the counts and proportions aggregated from the selected FP clinics. The variables to be abstracted from the FP register includes whether new or return FP client, HIV status, whether cervical cancer screening was conducted, what method of screening was used, what the results were, and if any referrals were made for this screening. This cascade will account for appropriate exits from the cascade (e.g. outside screening age range, or screened negative) and losses in the cascade (e.g. not screened, or positive screen not referred for follow-up).

Correlates of screening: Brief structured interviews with clinic managers as well as FP register data abstraction will collect information on for example, size of the FP clinic, staff, training of staff, age of FP clients, HIV status of clients, availability of FP commodities, level of experience of FP clinic manager, availability of cervical cancer screening commodities, referral practices, and any perceived barriers or facilitators of cervical cancer screening.

Cluster randomized trial: The primary outcome is the proportion of all FP clients aged 21-65 years who were screened for cervical cancer over the total number of eligible clients. These outcomes will be assessed every 3 months in the 12-month study period. We are requesting an additional 6 months for a total RCT study duration of 18 months. In-depth interviews will collect information about implementation of SAIA, barriers and facilitators to screening, and also using consolidated framework for implementation research (CFIR) constructs and domains.

Aim 3: Interviews with clinic managers and clinic observations along with data regarding time and expenses to implement SAIA will be collected. This will include general salary ranges for study staff and clinic staff, commodities needed, time for different clinic procedures, for example.

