Current screening practices vary between FP clinics: It is possible that randomization would select a disproportionate number of clinics in either intervention or control arms that already perform screening. This may bias results. Aim 1 results will be used to decide whether to stratify randomization based on past screening rates.

SAIA interventions not readily identifiable or feasible: Clinic staff may not identify solutions to address bottlenecks. In discussions with [name] (based on his experience with both CQI and the development of SAIA), this can be addressed by highly trained, experienced study staff to guide clinic staff through SAIA. Additionally, other quality improvement tools like root cause analysis and fishbone diagrams can be helpful (57). It is also possible that solutions proposed by staff members may not be feasible. Study staff will help staff to identify solutions that are more feasible in the given context and budget.

Focus on cervical cancer screening: This study will focus on increasing screening and will not address the linkage to treatment for positive screens. While we recognize that referral and treatment are also important, these steps would add complexity to this small study, and we likely would not have sufficient power. In addition, we felt that focusing on screening provided a useful metric for evaluating whether SAIA is potentially effective for addressing cervical cancer prevention. To insure adequate care during the study, we will partner with our Mombasa County collaborators to work programmatically to ensure that women with positive screens are linked to treatment. The extension of SAIA to improve linkage to treatment is a potential aim of a future study.

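### The Aim 2 GEE gives no role to each clinic's baseline screening proportion; pre-specify it as a covariate to guard against chance imbalance among 20 clinics

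*Combined protocol and SAP*

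**What the plan says.** The only account of the Aim 2 model is in Section E.6 (Data management, Aim 2). Generalized estimating equations, "clustered by clinic, will compare proportions screened in intervention versus control clinics longitudinally to account for correlation across time and between clinics", are applied to an outcome with this schedule: "These outcomes will be assessed every 3 months in the 12-month study period". Section E.7 adds: "We are requesting an additional 6 months for a total RCT study duration of 18 months". Neither section lists a covariate, a period term or an arm-by-period term, and Section E.7 names no adjustment variable for the trial although its title mentions confounders.

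Baseline screening is nevertheless measured. On the quantitative data for Aim 2, Section E.4 says: "These data will be collected at the beginning of the trial during a baseline period before any study procedures are completed". Collection then repeats every 3 months in all clinics.

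Randomisation is restricted on clinic size and location. Baseline screening enters only conditionally: "If facilities differ dramatically in cervical cancer screening rates at baseline, we will also stratify the randomization according to this factor". Section E.11 names the risk, "It is possible that randomization would select a disproportionate number of clinics in either intervention or control arms that already perform screening", adds that this could bias the results, and offers one remedy: "Aim 1 results will be used to decide whether to stratify randomization based on past screening rates". Neither place gives a measure, a threshold or strata.

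The preliminary data in C.1.E show how uneven clinics may be: "Of the 56 remaining clinics, 7 (13%) recorded any cervical cancer screening".

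**The concern.** With 10 clinics per arm, chance alone can leave the arms apart on baseline screening. If a clinic's baseline proportion predicts its follow-up proportion, part of that gap carries into the estimated arm difference. The usual protection is a baseline covariate fixed in advance. The data for it are already being collected, and the protocol already recognises the threat, but the model does not use them.

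The silence also leaves the analyst a choice. Baseline could be a covariate, a first outcome row, a change score or unused, and these do not give the same answer. A choice made after outcomes are seen would be post hoc.

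**Working it through.** **Inputs.** From Section E.5, Aim 2: 8% versus 20% screened, 183 clients per clinic, κ = 0.5, 10 clinics per arm, α = 0.05 (taken as two-sided). The text labels κ as cluster size variability, but it reproduces the stated power only as the between-clinic coefficient of variation of true proportions, so it is used that way here. The baseline-to-follow-up correlation r is not in the documents; a range of 0 to 0.7 is assumed.

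**1. The plan's own power.** V = 0.08·0.92/183 + 0.20·0.80/183 + 0.25·(0.08² + 0.20²) = 0.01288. Power = Φ(0.12·√(9/V) − 1.96) = 88.7%. The stated 90% is sound.

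**2. Size of a chance gap.** Variance of one clinic's observed baseline proportion: 0.08·0.92/183 + 0.25·0.08² = 0.002002. SD of the arm difference: √(2·0.002002/10) = 2.0 points. For a normal variable the largest fifth in absolute size averages 1.755 SD, so the gap there is 2.0·1.755 ≈ 3.5 points. This assumes allocation that does not balance on screening; restriction on size and location may reduce it by an unknown amount.

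**3. How much carries over.** With κ = 0.5 in both arms, true between-clinic SDs are 4 points (8%) and 10 points (20%). The slope of the arm difference on the baseline gap is r·(0.04·0.10 + 0.04·0.04)/(2·0.002002) = 1.40r. Times 3.5 points, this is about 4.9r: 1.5, 2.5 and 3.4 points at r = 0.3, 0.5 and 0.7. If the 12-point effect is additive, so that the intervention arm keeps the 4-point SD, the slope is r·(0.0016 + 0.0016)/(2·0.002002) = 0.80r, giving 0.8, 1.4 and 2.0 points.

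**4. Simulation** (40,000 trials per row; beta-distributed clinic proportions, κ = 0.5 in both arms, 183 clients at baseline and at follow-up; t-test on 18 df versus ANCOVA on 17 df). Each cell is without / with the covariate; error and RMSE are in percentage points.

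| r | Power, % | RMSE, all trials | Mean error, worst fifth | RMSE, worst fifth |
|---|---|---|---|---|
| 0 | 92 / 90 | – | – | – |
| 0.3 | 92 / 91 | 3.6 / 3.6 | 1.4 / under 0.1 | 3.8 / 3.8 |
| 0.5 | 92 / 94 | 3.6 / 3.4 | 2.4 / under 0.1 | 4.1 / 3.6 |
| 0.7 | 92 / 97 | 3.6 / 3.1 | 3.4 / under 0.1 | 4.7 / 3.3 |

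With an additive effect the simulated worst-fifth errors are 0.8, 1.4 and 1.9 points, in line with step 3. Type I error over all trials is close to 5% with or without the covariate. In the worst fifth it is 5.9%, 8.0% and 11.1% without the covariate at r = 0.3, 0.5 and 0.7, and 4.6% to 5.1% with it.

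**5. The same fix inside a GEE** (4,000 trials per row; logit link, four follow-up quarters with a constant clinic proportion assumed, Kauermann-Carroll correction). Power without / with the covariate is 96.2/95.0, 96.4/95.7, 96.4/97.3 and 96.5/99.2% at r = 0, 0.3, 0.5 and 0.7. The pattern is the same.

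**6. Few clinics screening at baseline.** With 12.5% of clinics at a mean of 8% and the rest at zero (overall 12.5%·8% = 1%), and follow-up as in step 4, power goes from 92.3 to 90.3, 92.3 to 90.8, 92.4 to 92.1 and 92.4 to 94.0% at r = 0, 0.3, 0.5 and 0.7. The covariate then helps power only at r = 0.7. At 7/56 per clinic, no clinic screens with probability (7/8)^20 = 7%.

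**The case against.** The strongest reply is that no error is shown. The test is valid, the estimate is unbiased over repeated randomisations, the power figure stands, and the benefit depends on an r that the documents do not give. That is correct, and it limits the point to a cheap improvement. The worst-fifth figures describe a selected subset; over all trials the accuracy gain is nil at r = 0.3 and modest above it. The larger carry-over figures also depend on the intervention arm having the wider clinic spread that κ = 0.5 at 20% implies.

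Three stronger readings are tempting, and the documents do not support them.

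- A reader might infer that clinics already screening are likely to fall in one arm. If 2, 3 or 4 of the 20 screen, 2·C(10,s)/C(20,s) gives 47%, 21% or 9%. But a few clinics screening and the rest at zero is an obvious case for the conditional stratification in Section E.4. Those odds apply only if that condition is not triggered.
- A reader might infer that the effect will be diluted. If the baseline quarter is an outcome row under an arm-only term, 12 points reads as 12·4/5 = 9.6 over 12 months or 12·6/7 = 10.3 over 18. That is one possible reading. Section E.4 sets the baseline period apart, and Section E.6 places the outcome in the study period.
- A reader might take the sparse case in step 6 as the expected one. It has control clinics rising from about 1% to 8% under usual procedures, and the documents describe no such rise. If controls stay at 1% and the intervention arm reaches 13%, the worst-fifth errors are 0.7, 1.2 and 1.8 points, and power is about 99.7% with or without the covariate.

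The undefined stratification trigger is mainly missing detail. It is decided on pre-randomisation data, so trial outcomes cannot steer it.

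**Conclusion.** The point holds as an omission in the primary model that is worth repairing. It is not a fault in validity or power. The benefit is protection against a chance baseline gap and against a post hoc choice of model, plus some precision if baseline predicts follow-up at about r = 0.5 or more. In the least balanced fifth of trials the covariate removes an average error of 1.4 to 3.4 points for r from 0.3 to 0.7, or 0.8 to 1.9 points if the effect is additive, against a planned effect of 12 points. Near r = 0.3 overall accuracy does not change, and at r = 0 there is a small loss. These sizes rest on κ = 0.5, 183 clients per clinic, an assumed r, and no balancing on baseline screening.

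**What to change.** **Section E.6.** State that the baseline quarter is a covariate and not an outcome row. Pre-specify the clinic's baseline screening proportion as a covariate in the primary GEE, with a small-sample correction suited to 20 clusters. Report the arm effect as a standardised risk difference, so that it matches the 12-point scale of the sample size section. Add a rule, fixed before outcome analysis, that replaces the proportion with an any/none indicator if few clinics screen at baseline, and drops the term if none does.

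**Section E.4, secondary.** The extension request suggests that the trial may already be running. If clinics are not yet randomised, make baseline screening (any versus none) a fixed factor in the restricted randomisation in place of the undefined condition. If they are, document whether the condition was applied and on which data.

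**Cost.** A few sentences, no new data and one of 18 degrees of freedom. Power falls by about 2 points if baseline is not prognostic (92% to 90%). Little or no power is gained if few clinics screen at baseline.

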7. VARIABLES – DEPENDENT, INDEPENDENT, CONFOUNDERS

Cervical cancer screening care cascade: The care cascade will examine the counts and proportions aggregated from the selected FP clinics. The variables to be abstracted from the FP register includes whether new or return FP client, HIV status, whether cervical cancer screening was conducted, what method of screening was used, what the results were, and if any referrals were made for this screening. This cascade will account for appropriate exits from the cascade (e.g. outside screening age range, or screened negative) and losses in the cascade (e.g. not screened, or positive screen not referred for follow-up).

Correlates of screening: Brief structured interviews with clinic managers as well as FP register data abstraction will collect information on for example, size of the FP clinic, staff, training of staff, age of FP clients, HIV status of clients, availability of FP commodities, level of experience of FP clinic manager, availability of cervical cancer screening commodities, referral practices, and any perceived barriers or facilitators of cervical cancer screening.

Cluster randomized trial: The primary outcome is the proportion of all FP clients aged 21-65 years who were screened for cervical cancer over the total number of eligible clients. These outcomes will be assessed every 3 months in the 12-month study period. We are requesting an additional 6 months for a total RCT study duration of 18 months. In-depth interviews will collect information about implementation of SAIA, barriers and facilitators to screening, and also using consolidated framework for implementation research (CFIR) constructs and domains.

Aim 3: Interviews with clinic managers and clinic observations along with data regarding time and expenses to implement SAIA will be collected. This will include general salary ranges for study staff and clinic staff, commodities needed, time for different clinic procedures, for example.

8. DATA COLLECTION INSTRUMENTS

For Aim 1, we will be abstracting quantitative data from the family planning registers. We will also collect basic information including, for example, clinic location, clinic environment (rural, peri-urban, urban), primary population served, number of women seen per day and number of new women to the clinic, for example.

In-depth interviews (IDIs) for the qualitative component of Aim 2 will be performed by trained study staff. This will follow a topic guide, and we anticipate asking open-ended questions about individual level, facility level and higher-level facilitators and barriers to cervical cancer screening of women presenting for family planning services. Examples of the most sensitive types of questions we would ask include:

- *What patient characteristics informed your decision of whether to offer cervical cancer screening or not?*
- *Describe how time limitations, financial limitations or staff conflicts/concerns affected your decision to offer cervical cancer screening.*

9. QUALITY ASSURANCE PROCEDURES

For quantitative data, data will be manually line-listed where the original images are compared to the soft copy data by a two-person team, with one reading data from the image documented and the other verifying the hard copy to ensure that registry abstraction match the soft-copy database. Incorrect data entries are revised based on re-evaluation of the digital image of the register. If necessary, we will go back to the original register (source document) to look at the data again and clarify response that could not be read clearly in the image. A record of incorrect entries is maintained. Following our data management SOP for the Women's Health Project in Mombasa, we will aim to have a data entry key-in error rate of less than 2 per 1000 entries, and monitor this periodically.

For the in-depth interviews (IDIs), a modified member check will be conducted by presenting the final key findings to a subgroup of clinic administrators and providers to assess completeness, salience, and relevance of our identified themes.

10. MATERIALS – EQUIPMENT AND SUPPLIERS

We anticipate performing in-depth interviews and group activities such as sequential process flow mapping with facility staff and managers either at their facilities (where feasible and desirable) or at our research clinic. Our research clinic is located at Ganjoni Health Center, and has multiple private interview rooms, a boardroom that accommodates 20, and a classroom that accommodates 40. The clinic has a DS-2 Olympus Digital Voice recorder and microphone suitable for both individual and group recording.

We have a central server, LAN, and fifteen computers in Mombasa (3 lab, 12 clinic/office). These are used for data entry, cleaning, analysis, administration, and communications. Two printers are located at the laboratory and three are located at the clinic.

We have 5 offices at Ganjoni clinic, which house the research, clinical, and administrative staff. A fully equipped and furnished boardroom (capacity=20) and classroom (capacity=40) with LAN, internet connection, large screen monitor, white board, blackboard, are available at the clinic for training and teaching activities.

There is one large office available at the laboratory at Coast Hospital, which is on the opposite side of town from Ganjoni Health Center. Depending on the location of activities with FP clinics in different areas, the study team may use the laboratory office for work or meetings when convenient.

We have 2 vehicles in Mombasa for project use, including staff and participant transport, logistical support, and supplies.

